### Sessions

The first study visit (V1) will take place approximately one week after the screening visit. Subjects will complete baseline questionnaires and will be randomized to one of the two groups. Subjects will be tested for exhaled air carbon monoxide, and saliva samples will be collected for analysis of smoking related chemicals (e.g., cotinine). Subjects will also complete questionnaires assessing their dependence on cigarettes (Fagerström Test for Nicotine Dependence (FTND) (Heatherton et al., 1991)), and rewarding effects of cigarettes (modified Cigarette Evaluation Questionnaire (Cappelleri et al., 2007)).

Subsequent study visits will occur approximately two weeks apart (with a five-day window on either side of the scheduled visit). If a participant does not attend a visit and it cannot be rescheduled within the allowable window, the visit will be considered a missed visit; if participants miss two consecutive visits they will be withdrawn from the study. Participants will be tested for exhaled air carbon monoxide, and will also complete questionnaires assessing their dependence on cigarettes (Fagerström Test for Nicotine Dependence (FTND) (Heatherton et al., 1991)), and rewarding effects of cigarettes (modified Cigarette Evaluation Questionnaire (Cappelleri et al., 2007)).

Questionnaires will be completed within REDCap on a desktop computer in the Center office. The technician will log on to the REDCap site and will open the questionnaires for the subjects. Subjects will only have access to their questionnaires. Access to any other websites will be blocked by Duke Psychiatry Information Technology.

At the first (V1) and final (V5) sessions, participants will provide saliva and urine samples. The saliva sample will be used for analysis of smoking related chemicals (e.g., cotinine). The urine sample will be used to assess total urinary 4-(methylnitrosamino)-1-(3-pyridyl)-1-butanol (NNAL), a metabolite of the tobacco-specific carcinogen 4-(methylnitrosamino)-1-(3-pyridyl)-1-butanone (NNK). The half-life of NNAL is 10 days (Goniewicz et al., 2009), yielding a valuable index of sustained reductions in cigarette smoking. The half-life of expired air CO, in contrast, is 4.5 h (Sandberg et al., 2011). Total urinary nicotine equivalents (a measure of total nicotine intake) will also be assessed.

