Randomization and E-cigarette Distribution: After the 1-week training/baseline period is complete and any concerns or questions about the CO monitoring have been addressed, the participants will be assigned a participant number that will determine their randomly assigned study condition, and will be sent by study staff the first shipment of study patches and e-cigarette devices and cartridges containing e-liquid corresponding to their group assignment (nicotine containing e-cigarettes vs. zero-nicotine e-cigarettes). Packages containing nicotine patches and e-cigarettes and liquids require signature by someone who is 21 years of age or older for delivery; the packages will not be delivered if no one appropriate is available to sign for them. This supply will be designed to last through the first 4 weeks of the study; if participants remain in the study, they will be sent a second shipment to use for the final 4 weeks.

Study Milestones: Remote participants will complete study milestones ("e-visits") that correspond to the study visits attended by local participants: baseline, week 2, week 4, week 6 and week 8, plus 4-week follow-up; they will take approximately one hour each to complete and include the same questionnaires that are completed at the in-person study visits, as well as a CO measurement at e-visit 5. The first (baseline) study milestone (V1) will take place after the participants receive their first shipment of e-cigarettes but before they start using them. At this time, participants will be called by study staff and given instructions on how to use the e-cigarettes. They will be asked to switch from cigarette use to use of e-cigarettes during the study. They will then be instructed on the use of daily self-report diaries to be completed on paper. In these diary entries, participants will record the number of conventional cigarettes smoked each day and the number of occasions of e-cigarette use (an occasion defined as taking at least one puff). Participants will be emailed a survey link to complete the questionnaires online via REDCap. Participants will have 72 hours to complete the survey until it expires and it is considered a "missed milestone"; if participants miss two consecutive milestones they will be withdrawn from the study. The

diary entries will be reported to the research staff by phone after e-visit online surveys have been completed.

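### A remote milestone finished between 72 hours and five days late counts as missed, the same delay in person is within the visit window, and both modes share one two-miss withdrawal rule

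*Combined protocol and SAP*

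**What the plan says.** **In person (Sessions).** Visits after the first are about two weeks apart, "with a five-day window on either side of the scheduled visit". If a participant does not attend and "it cannot be rescheduled within the allowable window, the visit will be considered a missed visit". Then "if participants miss two consecutive visits they will be withdrawn from the study".

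**Remote (Remote Study Participation, Study Milestones).** E-visits are described as milestones "that correspond to the study visits attended by local participants", at baseline and weeks 2, 4, 6 and 8 plus follow-up, using the same questionnaires. The link is emailed on the milestone date. "Participants will have 72 hours to complete the survey until it expires", and an expired survey is a missed milestone. Then "if participants miss two consecutive milestones they will be withdrawn from the study". No early window, grace period or rescheduling is described.

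**What hangs on e-visit 5.** Remote participants complete the questionnaires "as well as a CO measurement at e-visit 5"; their only other CO reading is at screening. They report diary entries by phone once the online survey is done. Under Return and Re-use of the CO monitor, the monitor for week 8 is sent to those accepted into the study who complete e-visits 1-4.

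**Analysis.** Data Analysis & Statistical Considerations sets the primary outcomes in the last week of the 8-week exposure, with expired CO as the main index of smoking. It gives no method for missed visits and does not name mode of participation as a covariate. The Data Safety Monitoring Plan requires only that missing data be recorded on a form.

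**The concern.** The two modes attach the same consequence, withdrawal, to different definitions of a miss, and the protocol does not explain why. A delay that leaves an in-person participant compliant can leave a remote participant with a missed milestone or, if repeated, out of the trial.

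The tighter rule applies to the mode with less CO data. In-person participants give a CO reading at every visit, so an earlier post-randomisation value exists if week 8 is lost. Remote participants have one post-randomisation reading, at e-visit 5. Since no method for missing data is stated, preventing avoidable misses is the main protection the plan has.

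**Working it through.** **1. The plan's own figure.** The only figure this could touch is 50 per group for at least 80% power (effect size 0.5, one-sided alpha 0.05).

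- n = 2(1.645 + 0.842)² / 0.5² = 49.5, rounded up to 50. The figure reproduces.
- Power at 50 = Φ(0.5·√(50/2) − 1.645) = Φ(0.855) = 80.4% (79.9% by noncentral t).
- Design Overview randomises 65 per group. Power at 65 = Φ(0.5·√(65/2) − 1.645) = 88.6%.
- Loss that can be absorbed before reaching 50: (65 − 50)/65 = 23.1%.

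**2. The two rules side by side.**

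| | In person | Remote |
|---|---|---|
| Latest allowed | 5 days after the date | 72 hours after the link |
| Rescheduling | Yes, inside the window | None described |
| Withdrawal | Two consecutive misses | Two consecutive misses |

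The relevant contrast is 5 days against 3. The five early days in person do not bear on late completion. The band treated differently is 5 × 24 − 72 = 48 hours. Completion four days late at visits 3 and 4 gives no miss in person; remotely it gives two consecutive misses and withdrawal. This follows from the text alone.

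**3. From a late survey to a lost CO reading.** The 72-hour expiry is written for the survey. A lost week-8 CO reading needs one of three further steps:

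- the whole of milestone 5 is treated as missed once its survey expires;
- the participant has already been withdrawn after two consecutive misses;
- the e-visits 1-4 condition is applied literally, so that one earlier expired survey means no monitor is sent.

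**4. Illustrative size.** Let q be the chance that a remote milestone is finished inside the 48-hour band. The documents do not give it. Assume 2% to 20%, independent across V2 to V5, with no other losses.

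- Two consecutive misses in V2-V5: 3q² − 2q³
- Milestone 5 late, or already withdrawn: q + (1 − q)(2q² − q³)
- At least one miss in V2-V4: 1 − (1 − q)³

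| q | Two consecutive misses | Milestone 5 lost | Any miss V2-V4 |
|---|---|---|---|
| 2% | 0.1% | 2.1% | 5.9% |
| 5% | 0.7% | 5.5% | 14.3% |
| 10% | 2.8% | 11.7% | 27.1% |
| 20% | 10.4% | 25.8% | 48.8% |

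The percentages are of remote participants, not of the trial. If lateness clusters in the same people, then for a given q the first column rises and the last falls.

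**5. Effect on power.** With a remote share r and a loss L from the table, n per group = 65(1 − rL). The share is not given; assume 10% to 50%.

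- Only milestone 5 losses count: n runs from 64.9 to 65(1 − 0.5 × 0.2576) = 56.6, and power from 88.5% to 84.5%.
- Any miss in V2-V4 removes the CO reading: n runs from 64.6 to 65(1 − 0.5 × 0.488) = 49.1, and power from 88.4% to 79.8%.

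**The case against.** A window that differs by mode can be defended. An in-person visit needs travel and an appointment; an online survey needs neither. The statement that e-visits correspond to visits lists time points and questionnaires and does not promise equal windows. This has force, but the protocol does not give that reason, and it would not explain why the same withdrawal rule rests on the shorter limit.

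A reader might infer that a late e-visit 5 forfeits the primary CO reading. The documents do not say so. The CO reading is taken by Zoom, diaries go by phone and samples by courier, and no section refuses any of these because a survey link has expired. A single late e-visit 5 also withdraws nobody. This objection stands, and it limits the point to the routes in step 3 of the working.

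A reader might also infer bias between the arms. The rule is the same in both groups, and the planned comparison is between groups, not modes. The arms would be affected unequally only if lateness differed by arm, on which the documents are silent.

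Finally, a longer window has costs. CO has a stated half-life of 4.5 hours and supplies are sent for two four-week blocks, so a reading several days late may reflect behaviour after the exposure period. The Side Effects Form is completed online at milestones, so a later survey could delay its review. People may also simply delay further when given more time. The first two costs are real and the fix must address them; the third means the gain could be smaller than the table in the working suggests.

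**Conclusion.** The discrepancy is real and minor. Between 72 hours and five days, the same lateness is a miss remotely and compliant in person, and two in a row lead to withdrawal only in the remote mode. It does not affect remote participants who answer within 72 hours or those later than five days.

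Its size cannot be derived from the documents. The 0.1% to 10.4% reaching two consecutive misses, and the other ranges shown, rest on an assumed q, independence between milestones and no other attrition.

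It would be too strong to conclude that the trial is underpowered. With 65 per group against 50 needed, power stays above 84% when only milestone 5 losses count. It falls just under 80% only in the most extreme combination: half the participants remote, 20% of milestones in the band, and the e-visits 1-4 condition read literally. Other attrition would draw on the same margin. That condition is the most direct textual route to a lost week-8 CO reading, because one earlier miss is enough.

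**What to change.** In Study Milestones:

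- Keep the REDCap link open until five days after the milestone date, and count a milestone as missed only after that.
- Send a reminder at 72 hours together with a staff contact, so that review of the Side Effects Form does not wait for the survey.
- State that the e-visit 5 Zoom CO reading and diary report may be collected within the same window whether or not the survey was completed on time, with the actual date recorded.

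Reconcile the e-visits 1-4 condition under Return and Re-use of the CO monitor with Study Milestones, so that one earlier missed survey does not forfeit the week-8 CO reading. The two-consecutive-miss rule itself need not change.

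The cost is a link-expiry setting, a reminder with a staff contact, and some wording. The downside is up to two more days' spread in remote assessment timing (5 − 3), including a CO reading that may fall a few days after week 8. The Sessions section already accepts that spread for in-person visits.

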Each subsequent study milestone (V2-V5) will occur 2 weeks after the previous one, with the follow-up milestone occurring 4 weeks after milestone 5. Participants will be sent a link by email on each study milestone date with instructions to complete the REDCap questionnaires. After the second milestone is completed, participants will be sent a second shipment of e-cigarette cartridges to use until the end of study. At the time of the baseline and final milestones (V1 and V5) and follow-up, participants will be asked to collect a urine sample for NNAL analysis and a saliva sample for analysis of smoking related chemicals (e.g., cotinine), and send these samples to the Duke CSC via UPS.

Participants will be called within 3 days after the first day of study intervention to make sure the study products are being used as directed as well as to ask about any study related side effects. Any reports of side effects, in addition to responses to the Side Effects Form completed online at the study milestones, will be reviewed by the study medical provider. The provider will call the participant if any of the side effects require follow up.

Return and Re-use of the CO monitor: Participants will be asked to return the CO monitor after the CO reading has been obtained during the screening process. If they are accepted into the study and complete e-visits 1-4, then a CO monitor will be sent to them to obtain the CO reading at e-visit 5. The participant will be asked to return the CO monitor after e-visit 5. Upon return of the CO monitor, research staff will disinfect the monitor before sending it to another participant.

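### As worded, a remote participant who misses one e-visit but stays enrolled has no stated route to a week-8 CO reading, the main smoking index

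*Combined protocol and SAP*

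**What the plan says.** The Data Analysis & Statistical Considerations section sets the primary outcomes in the final week of the 8-week exposure and makes expired CO the main measure of combustible smoking. NNAL and diary cigarettes per day are secondary.

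For remote participants, the Remote Study Participation section says the following:

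- CO is taken at screening and at e-visit 5 only. The Study Milestones paragraph lists the e-visit content "as well as a CO measurement at e-visit 5", with no condition attached.
- The monitor is returned after the screening reading. On the second monitor, the paragraph on its return and re-use says: "If they are accepted into the study and complete e-visits 1-4, then a CO monitor will be sent to them".
- "Participants will have 72 hours to complete the survey until it expires", after which the milestone counts as missed; "if participants miss two consecutive milestones they will be withdrawn from the study".
- Diaries record cigarettes and "the number of occasions of e-cigarette use", and the "diary entries will be reported to the research staff by phone after e-visit online surveys have been completed".
- The second product shipment is described in two ways: "if participants remain in the study, they will be sent a second shipment to use for the final 4 weeks", and "After the second milestone is completed, participants will be sent a second shipment of e-cigarette cartridges".

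For in-person participants, the Sessions section provides a CO test at each visit, a window of five days either side and the same two-consecutive-miss withdrawal rule. The Four-week Follow-up section adds a further CO reading. None is listed for remote participants at follow-up.

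**The concern.** The withdrawal rule and the monitor rule do not cover the same people. Missing one e-visit, or two that are not adjacent, does not end participation, but it takes the participant outside the only stated provision for a second monitor. The first monitor has already gone back and no later remote CO is scheduled, so that person has no stated route to any CO reading after randomisation.

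All four gating e-visits come after randomisation. Remote participants are assigned and sent product before e-visit 1, and e-visits 2 to 4 fall while they are using the assigned product. On a literal reading, whether the main smoking index is collected depends on behaviour that treatment could influence. Those with a week-8 CO could then be a selected subset, possibly selected differently in the two arms. An in-person participant with the same single miss is still CO-tested at later visits, so the gap is specific to the remote mode.

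The analysis section gives no method for missing values, and the Data Safety Monitoring Plan provides only for Missing Data Forms. Because remote diaries are phoned in once surveys are done, the self-report backup may also be affected by a missed survey, although the text does not say that it is lost.

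**Working it through.** **1. The text.** Of the 16 complete/miss patterns over e-visits 1 to 4:

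- 1 has no miss, so the participant meets the stated condition for a monitor;
- 8 contain two adjacent misses, so the participant is withdrawn;
- 7 contain at least one miss but no two adjacent, so the participant is enrolled and outside the condition.

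No other paragraph provides for a second monitor. The gap is therefore real as a matter of wording.

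**2. The plan's own power figure.** Inputs from the analysis section are effect size 0.5, one-tailed alpha 0.05 and 50 per group. The normal approximation gives 0.804 and the noncentral t gives 0.799, which agrees with the stated 80%. At the 65 per group to be randomised, the noncentral t gives 0.883. The cushion is (65 − 50)/65 = 23%.

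**3. Illustration of size.** The documents give no miss rate, no clustering and no remote share, so all three are assumed. Each of e-visits 2 to 5 is missed with probability p, e-visit 1 is completed, and a missed e-visit 5 yields no CO. Define:

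- W, withdrawn before e-visit 5 (misses at 2 and 3, or at 3 and 4) = 2p² − p³
- E, still enrolled but with a miss at 2 to 4, so no monitor = 1 − (1 − p)³ − W
- A, the part of E due to the clause because e-visit 5 would have been completed = E(1 − p)
- F, only e-visit 5 missed = p(1 − p)³

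No week-8 CO with the clause = W + E + F. Without the clause = W + (E − A) + F.

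These formulas are for independent misses. At p = 0.10: W = 0.020 − 0.001 = 0.019; E = 1 − 0.729 − 0.019 = 0.252; A = 0.252 × 0.9 = 0.227; F = 0.1 × 0.729 = 0.073. For correlated misses, the same patterns are weighted by a beta-binomial with intraclass correlation (ICC) 0.3.

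| Misses | p | W | E | A | F | No CO, with clause | No CO, without |
|---|---|---|---|---|---|---|---|
| Independent | 0.05 | 0.005 | 0.138 | 0.131 | 0.043 | 0.185 | 0.055 |
| Independent | 0.10 | 0.019 | 0.252 | 0.227 | 0.073 | 0.344 | 0.117 |
| Independent | 0.20 | 0.072 | 0.416 | 0.333 | 0.102 | 0.590 | 0.258 |
| ICC 0.3 | 0.05 | 0.025 | 0.083 | 0.064 | 0.020 | 0.127 | 0.064 |
| ICC 0.3 | 0.10 | 0.055 | 0.153 | 0.114 | 0.035 | 0.243 | 0.128 |
| ICC 0.3 | 0.20 | 0.126 | 0.260 | 0.182 | 0.054 | 0.440 | 0.258 |
| Complete clustering | any | p | 0 | 0 | 0 | p | p |

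**4. People.** At p = 0.10 with half of 130 remote, the clause accounts for 65 × 0.227 = 14.7 people (independent), 65 × 0.114 = 7.4 (ICC 0.3) or 0 (complete clustering). At ICC 0.3, a 25% remote share gives 32.5 × 0.114 = 3.7 and a 10% share gives 13 × 0.114 = 1.5.

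**5. Power.** Two-sample t-test, covariates ignored, n per arm = (130 − 130 × share × missing)/2. At p = 0.10 and share 0.50:

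- Independent: 53.8 per arm with the clause against 61.2 without; power 0.824 against 0.865.
- ICC 0.3: 57.1 against 60.8; power 0.844 against 0.864.

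Power with the clause falls below 0.80 only at harsher inputs: 0.786 against 0.856 without it (p = 0.10, independent, share 0.75), and 0.767 against 0.841 (p = 0.20, independent, share 0.50).

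**The case against.** The strongest reply is that the sentence says if, not only if. It sits in a paragraph about returning and re-using monitors, and the e-visit 5 CO is planned elsewhere without condition. Completing e-visits 1 to 4 may simply mean reaching e-visit 5 still enrolled. The second product shipment is described just as loosely, and the compensation section pays for returning the monitor at study end without an e-visit condition. This stands as a plausible account of intent. It does not remove the conflict, because the protocol gives a missed milestone a specific definition and staff following the monitor paragraph literally could withhold a monitor.

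Second, the illustrated effect runs from nothing to a third of remote participants on invented inputs, and power barely moves in the main case. That is correct. The figures show only that the effect need not be negligible. Bias is possible, not demonstrated.

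Third, urine and saliva at the final e-visit are requested regardless of earlier e-visits, so objective data would remain. That is also true, but NNAL is a secondary measure and does not replace the main index.

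Fourth, contacting people whom the protocol calls withdrawn goes beyond a wording fix and depends on consent text that is not available here. The point is fair as to cost. Staff withdrawal for missed visits is nevertheless not withdrawal of consent, and it creates the same kind of selective loss in both modes.

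**Conclusion.** The concern holds as a conflict in the text. A remote participant with one miss, or non-adjacent misses, among e-visits 1 to 4 remains enrolled without a stated route to the week-8 CO. Read literally, the provision makes collection of a primary outcome depend on post-randomisation compliance.

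The size is uncertain. At an assumed 10% miss rate, the share of remote participants without a week-8 CO is 34% with the clause against 12% without it if misses are independent, 24% against 13% at ICC 0.3, and 10% either way under complete clustering. These figures also assume that e-visit 1 is completed. The direction of any bias, and any difference between arms, cannot be derived from the documents. The argument rests on selective missingness and not on power. It should be fixed, with medium confidence, because the sponsor may never have intended the restriction.

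**What to change.** - Reconcile the Remote Study Participation paragraphs so that the e-visit 5 monitor goes to every randomised remote participant who has not withdrawn consent, whatever e-visits were missed.
- Reword the two-miss rules for both modes so that they do not end outcome collection. Still seek the week-8 CO, urine, saliva and last-week diary, and analyse these participants in their assigned arm. This concerns outcome collection only. The two descriptions of the second product shipment also need reconciling, but no view is taken here on product supply.
- Report the number with a week-8 CO by arm and by mode (in-person or remote), with reasons for absence taken from the Missing Data Forms.

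The cost is protocol wording, some extra shipments of re-used monitors and one table, plus a check that the consent form allows contact after missed visits. The main downside is a higher chance of losing a monitor valued at $620 to a less engaged participant, partly offset by the existing $50 return payment. Some of those who missed e-visits will still not respond, so the change reduces selective missingness but does not remove it.
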